### **2.7.1.1 Adverse events of special interest / grouping of AEs**

In this section the Adverse Events of Special Interest (AESI), safety risks as defined in the Safety Profiling Plan (SPP) and Risk Management Plan (RMP) and their targeted analyses will be described. Each risk consist of one or more well-defined safety events which are similar in nature and for which there is a specific clinical or safety interest in connection with the study treatment.

All AE grouping will be stored in the Compound Case Retrieval Strategy sheet (CRS) with clear versioning and reference to the MedDRA version used.

All AESIs will exclusively be based on adverse events only. The case retrieval sheet contains all MedDRA terms which need to be considered for case retrieval (NMQs, HLGTS, PTs, etc.). Note that certain adverse events may be reported within multiple groupings.

All AESI definitions or AE grouping need to be specified in the CRS. If a CRS update is necessary, the final version needs to be available in a reasonable time ahead of the DBL. The CRS version will be included in a footnote of the AESI tables. Table 2-5 provides AESI groupings per latest CRS. The most up-to-date version of the CRS will be used at the time of the analysis.

**Table 2-5      AESI groupings**

AESI grouping	MedDRA category
Anemia	SMQ
Diarrhea	SMQ
Hepatobiliary toxicity	SMQ
Infections	SMQ and SOC
Leukopenia	HLT
Nausea, emesis	HLT
Neutropenia	HLT and PT
Pulmonary embolism	SMQ and HLT
QTc interval prolongation	SMQ
Renal impairment	SMQ
Reproductive toxicity	SMQ
Thrombocytopenia	SMQ

### **Data analysis of AESIs**

An adverse event of special interest is a grouping of adverse events that are of scientific and medical concern specific to compound ribociclib. These groupings are defined using MedDRA terms, SMQs (standardized MedDRA queries), HGLTs (high level group terms), HLT (high level terms) and PTs (preferred terms). Customized SMQs (Novartis MedDRA queries, NMQ) may also be used. An NMQ is a customized group of search terms which defines a medical concept for which there is no official SMQ available or the available SMQ does not completely fit the need. It may include a combination of single terms and/or an existing SMQ, narrow or broad. For each specified AESI, number and percentage of patients with at least one event of the AESI occurring during on treatment period will be summarized.

#### **2.7.2      Deaths**

Separate summaries for on-treatment and all deaths (including post-treatment death) will be produced by treatment arm, system organ class and preferred term.

All deaths will be listed, post treatment deaths will be flagged.

Note: “Study indication” as primary reason of death should be coded using MedDRA terms based on the diagnosis CRF field at start of study. If not coded accordingly in the database, it still must be included in the summary table. Coded reasons for deaths will then be summarized by category ‘Study indication’ and ‘Other’ (as selected by the investigator).

#### **2.7.3      Laboratory data**

On analyzing laboratory data, data from all sources (central and local laboratories) will be combined. The summaries will include all assessments available for the lab parameter collected no later than 30 days after the last study treatment administration date (see Section 2.1.1).

Grading of laboratory values will be assigned programmatically as per National Cancer Institute CTCAE version 4.03. The calculation of CTCAE grades will be based on the observed laboratory values only, clinical assessments will not be taken into account.

CTCAE Grade 0 will be assigned for all non-missing values not graded as 1 or higher. Grade 5 will not be used.

For laboratory tests where grades are not defined by CTCAE, results will be categorized as low/normal/high based on laboratory normal ranges.

For hematology: Absolute neutrophils, Absolute granulocytes, Hemoglobin, WBC, Platelet counts, PTT.

For Biochemistry: Albumin, Alkaline phosphatase, **Blood Creatinine**, SGPT (ALT), Amylase, SGOT (AST, Total bilirubin, Calcium (hyper & hypo), GGT, Glucose (hyper & hypo), Lipase, Magnesium (hyper & hypo), Phosphate, Potassium (hyper & hypo), Sodium (hyper & hypo).

For both groups of laboratory tests, shift tables to compare baseline to the worst postbaseline value will be produced using CTCAE grade and normal range.

A single listing for all the laboratory parameters with grades, normal ranges and lab values flagged to indicate that the values are outside the normal range will be reported.

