**Document History – Changes compared to previous final version of SAP**

Date	Time Point	Reasons for update	Outocme for update	Section and title impacted (Current)
31-May-2017	Before DBL	First Version		
01-May-2019	Before DBL	The trial had an early enrollment closure on 12 February 2018; the protocol was amended on April 2018.	The study is now a Phase II trial. All sections related to Efficacy analysis has been removed.  Efficacy data will be summarized by a listing only.	All the sections of the earlier version has been impacted
23-Feb-2020	Before DBL	
 
1. Add one lab param for the shift table.
 
2. Clarify which CRS version will be used.
 
3. For exposure data, GnRH agonist will be combined with ET to report.
 
	
 
1. Blood Creatinine was added to report.
 
2. Added a sentence to use the most up-to-date CRS.
 
3. For exposure data, GnRH was combined with ET to report.
 
	
 
1. Section 4.3
 
2. section 2.7.1.1
 
3. section 2.4.1
 

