**Table 1-1 Objectives and related endpoint**

Objective	Endpoint
Primary To evaluate the preliminary safety and tolerability of the ribociclib + ET in patients that were randomized to ribociclib + ET prior to the early closure of enrollment.	Tolerability and Safety of the treatment regimen based on frequency and severity of AEs, laboratory and ECG abnormalities

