Lymphocytes  ↓	10  /L	LYM		≥ 1.5x10  /L	< 1.5 - 0.8 x 10  /L	< 0.8 - 0.5 x 10  /L	< 0.5 - 0.2 x 10  /L	< 0.2 x 10  /L
Lymphocytes ↑	10  /L	LYM			-	> 4 - 20 x 10  /L	> 20 x 10  /L	-
Biochemistry								
AST ↑	U/L	AST	0 - 35 U/L or 0 – 0.58 ukat/L (60 x ukat/L = U/L)	≤ ULN	> ULN - 3.0 x ULN	> 3.0 - 5.0 x ULN	> 5.0 - 20.0 x ULN	> 20.0 x ULN
ALT ↑	U/L	ALT	0 - 35 U/L or 0 – 0.58 ukat/L (60 x ukat/L = U/L)	≤ ULN	> ULN - 3.0 x ULN	> 3.0 - 5.0 x ULN	> 5.0 - 20.0 x ULN	> 20.0 x ULN
Total bilirubin ↑	umol/L	BILI	5.1 – 20.5 umol/L or 0.3 – 1.2 mg/dL (17.1 x mg/dL = umol/L)	≤ ULN	> ULN - 1.5 x ULN	> 1.5 - 3.0 x ULN	> 3.0 - 10.0 x ULN	> 10.0 x ULN
Alk. Phosphatase ↑	U/L	ALP	36 - 92 U/L or 0.5 - 1.5 ukat/L (60 x ukat/L = U/L)	≤ ULN	> ULN - 2.5 x ULN	> 2.5 - 5.0 x ULN	> 5.0 - 20.0 x ULN	> 20.0 x ULN
Creatinine  ↑	umol/L	CREAT	61.9 - 115 umol/L or 0.7 – 1.3 mg/dL (88.4 x mg/dL = umol/L)	≤ ULN	> ULN - 1.5 x ULN	> 1.5 - 3.0 x ULN	> 3.0 - 6.0 x ULN	> 6.0 x ULN
Creatinine kinase  ↑	U/L	CK	30 - 170 U/L or 0.5 – 2.83 ukat/L (60 x ukat/L = U/L)	≤ ULN	> ULN - 2.5 x ULN	> 2.5 - 5.0 x ULN	> 5.0 - 10.0 x ULN	> 10.0 x ULN
Albumin  (Hypoalbuminemia)	g/L	ALB	35 - 55 g/L or 3.5 to 5.5 g/dL	≥ LLN	< LLN - 30 g/L	< 30 - 20 g/L	< 20 g/L	-
Total Cholesterol ↑	mmol/L	CHOL	3.88 – 5.15 mmol/L or 150 - 199 mg/dL (38.67 x mg/dL = mmol/L)	≤ ULN	> ULN - 7.75 mmol/L > ULN - 300 mg/dL	> 7.75 - 10.34 mmol/L > 300 – 400 mg/dL	> 10.34-12.92 mmol/L > 400 – 500 mg/dL	> 12.92 mmol/L > 500 mg/dL
Lipase ↑	U/L	LIPASE	<95 U/L or <1.58 ukat/L (60 x ukat/L = U/L)	≤ ULN	> ULN - 1.5 x ULN	> 1.5 - 2.0 x ULN	> 2.0 - 5.0 x ULN	> 5.0 x ULN
Amylase ↑	U/L	AMYLASE	0 - 130 U/L or 0 – 2.17 ukat/L (60 x ukat/L = U/L)	≤ ULN	> ULN - 1.5 x ULN	> 1.5 - 2.0 x ULN	> 2.0 - 5.0 x ULN	> 5.0 x ULN
Uric acid  (Hyperuricemia)	umol/L	URATE	150 - 470 umol/L or 2.5 – 8 mg/dL (59.48 x mg/dL = umol/L)	≤ ULN	> ULN – 10 mg/dL > ULN – 595 umol/L	-	-	> 10 mg/dL > 595 umol/L

ULN = Upper Limit of Normal range; LLN = Lower Limit of Normal range

LAB - CTC grades in Novartis Oncology (26Oct15)

CTC grades for laboratory values in Novartis Oncology (based on CTCAE v4.03 – June 2010)

Page 2

Lab test (toxicity)	SI unit	Lab test (NCDS)	Normal ranges (Merck manual, July 2015) and conversion factors	CTC Grades 				
				0	1	2	3	4

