## Imputation Rules

CTC grading for blood differentials is based on absolute values. However, this data may not be reported as absolute counts but rather as percentage of WBC.

If laboratory values are provided as '<X' (i.e. below limit of detection) or '>X', prior to conversion of laboratory values to SI unit, these numeric values are set to X.

The following rules will be applied to derive the WBC differential counts when only percentages are available for a xxx differential

$$\text{xxx count} = (\text{WBC count}) * (\text{xxx \%value} / 100)$$

Further derivation of laboratory parameters might be required for CTCAE grading. For instance, corrected calcium can be derived using the reported total calcium value and albumin at the same assessment using the following formula:

$$\text{Corrected Calcium (mg/dL)} = \text{Calcium (mg/dL)} - 0.8 [\text{Albumin (g/dL)} - 4]$$

In order to apply the above formula, albumin values in g/L will be converted to g/dL by multiplying by 0.1), calcium values in mmol/L will be converted to mg/dL by dividing by 0.2495. For calculation of laboratory CTC grades 0 and 1, the normal range for derived corrected calcium is set to the same limits (in mg/dL) as for calcium.

CTC grades for the derived absolute WBC differential counts (neutrophils, lymphocytes) and corrected calcium will be assigned as described above for grading.

Estimated glomerular filtration rate (eGFR) will be calculated using Cockcroft-Gault formula:

$$eGFR = \frac{(140 - Age) \times Mass(in\ kilograms) \times [0.85\ if\ Female]}{72 \times Serum\ Creatinine\ (in\ mg/dL)}$$

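### Lymphocytes are to be graded under Section 4.3 but are missing from the hematology shift-table list in Section 2.7.3, so laboratory-graded lymphocyte abnormalities would be listed but not tabulated

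*SAP*

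**What the plan says.** The SAP's primary endpoint is tolerability and safety, judged by "frequency and severity of AEs, laboratory and ECG abnormalities" (Table 1-1, repeated in Section 2.4.2).

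Section 2.7.3 gives two parameter lists, one for hematology and one for biochemistry. The hematology list reads: "For hematology: Absolute neutrophils, Absolute granulocytes, Hemoglobin, WBC, Platelet counts, PTT". For both groups, "shift tables to compare baseline to the worst postbaseline value will be produced using CTCAE grade and normal range". The section also plans one by-patient listing of all laboratory parameters with their grades. The only other laboratory table is the liver-function summary, which has no hematology content.

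Section 4.3 reproduces the sponsor's grading table, which gives limits for low and for high lymphocytes. Its imputation rules convert percentage differentials to absolute counts and then state: "CTC grades for the derived absolute WBC differential counts (neutrophils, lymphocytes) and corrected calcium will be assigned as described above for grading". Section 4.3 also requires tests graded in both directions to be summarized separately and labelled by direction.

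The Document History for the February 2020 version records the request "Add one lab param for the shift table" and its outcome, "Blood Creatinine was added to report".

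**The concern.** Section 4.3 names two differential counts to be graded, neutrophils and lymphocytes. Neutrophils reach a shift table and lymphocytes do not. The study is now descriptive, and its single objective is safety, so the tables are its main output. A grade 3 or 4 lymphocyte count on treatment would enter no laboratory table. A reader of the study report would have to count such patients by hand from a listing, while the other graded hematology analytes would each have a table of baseline against worst post-baseline grade.

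**Working it through.** No sample size, error rate or event count is involved, so the check sets the sections side by side and applies the SAP's grade limits to one illustrative patient.

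**1. Is the Section 2.7.3 list the shift-table list?** It stands directly before the shift-table sentence, which refers to both groups of tests. The Document History shows that getting a parameter into the shift table took a SAP update. The history gives the affected section as 4.3, but the parameter list that now shows blood creatinine, in bold, is the one in Section 2.7.3. Treating that list as closed is the natural reading.

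**2. Graded hematology analytes against the list.**

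| Analyte graded in the 4.3 hematology block | Directions graded | In the 2.7.3 list |
|---|---|---|
| WBC | low, high | yes |
| Hemoglobin | low, high | yes |
| Platelets | low | yes |
| Neutrophils | low | yes |
| Lymphocytes | low, high | **no** |

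Four of five analytes are listed. By graded line the total is 2 + 2 + 1 + 1 + 2 = 8, and the two lymphocyte lines are missing.

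**3. Where lymphocyte results would still appear.**
- Laboratory grades: the by-patient listing only.
- Investigator-reported lymphopenia: the AE tables by system organ class and preferred term, where repeated grades of a term count under the maximum grade (Section 2.7.1).

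These are different measurements. Laboratory grades come from observed values alone, without clinical assessment (Section 2.7.3). AE tables depend on what the investigator reported. The groupings of special interest also rest only on AEs (Section 2.7.1.1).

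**4. Can the listed white-cell parameters stand in?** Take an illustrative patient, in x10^9/L, with the WBC reference range printed in Section 4.3 (lower limit 3.9):
- WBC 4.0, at or above 3.9: grade 0.
- Neutrophils 3.4, at or above 2: grade 0.
- Lymphocytes 0.4, below 0.5 and not below 0.2: grade 3.

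The counts are compatible: 3.4 + 0.4 = 3.8, which leaves 4.0 - 3.8 = 0.2 for other white cells. This patient is normal in both white-cell shift tables and has grade 3 lymphopenia.

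The high direction has the same gap. Lymphocytes above 4 and up to 20 are grade 2, while the only graded high category for WBC starts above 100.

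**The case against.** **The lymphocyte grades are not lost.** A reader might infer that lymphopenia is never tabulated in this study. The SAP does not support that. Lymphopenia reported as an AE is counted by preferred term, and every laboratory grade is listed. The gap is confined to laboratory-graded abnormalities in tables.

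**There is no outright contradiction.** Section 4.3 promises grades, not a table, and grading for a listing is consistent with leaving the parameter out of the shift tables. Section 4.3 also gives an eGFR formula although eGFR is not in the Section 2.7.3 lists, so a derivation here does not guarantee a summary. This stands. The point is a gap against the primary endpoint, not two statements that cannot both be true.

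**The grading table is a sponsor-wide standard.** It also grades creatine kinase, cholesterol, uric acid, triglyceride, INR and fibrinogen, none of which is in the Section 2.7.3 lists. A lymphocyte row in that table is therefore weak evidence of oversight. Two things weigh more: the Section 4.3 sentence that names lymphocytes beside neutrophils, and the fact that the other unlisted tests are biochemistry or coagulation. Within hematology, lymphocytes are the only omission.

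**The creatinine update can be read either way.** It shows that the list can be extended cheaply before database lock. It also shows that the sponsor reopened the list and added one parameter only, which fits a deliberate choice. It does not prove that the lymphocyte omission is an error.

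**Absolute granulocytes are no defect.** A reader might object that they are listed without a grading row. Section 2.7.3 provides for ungraded tests by low, normal and high categories, so that criticism fails.

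**Collection is not confirmed.** The SAP does not say that lymphocytes were collected, and the protocol is not at hand. This stands as a condition on the fix.

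**Conclusion.** The point holds in a limited form. Followed as written, the SAP produces no frequency or severity table for laboratory-graded lymphocyte abnormalities, in either direction, although laboratory abnormalities are part of the primary endpoint. One of five graded hematology analytes is affected, and the WBC and neutrophil tables can miss grade 3 lymphopenia altogether.

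The importance is low. The study is descriptive, no test or estimate depends on this row, and the values remain in the listing. How many patients would be affected cannot be judged from the SAP. The conclusion assumes that the Section 2.7.3 list is closed and that the white-cell differential was collected. Whether the omission was an oversight or a choice is not stated.

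**What to change.** Add absolute lymphocytes (low and high) to the hematology list in Section 2.7.3. Grade them with the limits already in Section 4.3 and summarize each direction separately, as that section requires. If lymphocytes are meant for the listing only, say so in Section 2.7.3 and give the reason. If the differential was not collected, remove lymphocytes from the Section 4.3 sentence that promises their grades.

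The cost is one more parameter, in two directions, in a table already planned. The derivation and grading rules exist, and no new data are needed if the differential was collected.

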### **Liver function parameters**

Liver function parameters of interest are total bilirubin (TBL), ALT, AST and alkaline phosphatase (ALP). The number (%) of patients with worst post-baseline values as per Novartis Liver Toxicity guidelines will be summarized:

The following summaries will be produced:

- ALT or AST > 3xULN
- ALT or AST > 5xULN
- ALT or AST > 8xULN
- ALT or AST > 10xULN
- ALT or AST > 20xULN
- TBL > ULN
- TBL > 2xULN
- TBL > 3xULN
- ALP > 1.5xULN
- ALP > 2xULN
- ALP > 3xULN
- ALP > 5xULN
- ALP > 8xULN

- ALP > 10xULN
- Combined categories of ALT/AST and total bilirubin: e.g., ALT or AST > 3xULN & TBL > 2xULN
- ALT or AST > 3xULN & TBL > 2xULN & ALP < 2xULN (biochemistry Hy's law)

## **2.7.4 Other safety data**

### **2.7.4.1 ECG data**

#### **Data handling**

The study requires ECG triplicates at any assessment, so the average of the ECG parameters at that assessment will be used in the analyses. For unscheduled assessments, 15-minute windows will be applied to group assessments for averaging.

#### **Data analysis**

12-lead ECGs including PR, QRS, QT, QTcF, and RR intervals will be obtained for each subject during the study. ECG data will be read and interpreted centrally.

ECG data will be summarized by presenting summary statistics of the raw data and change from baseline by treatment group and time point. The following parameters will be assessed: QTcF, QT, PR, and QRS intervals in msec, heart rate (bpm), and RR. Shift table will be presented for QTcF and QT by treatment arm.

The number and percentage of subjects with notable ECG values will be presented by treatment arm.

- QT, QTcF
  - New value of > 450 and  $\leq$  480 ms
  - New value of > 480 and  $\leq$  500 ms
  - New value of > 500 ms
  - Increase from Baseline of > 30 ms to  $\leq$  60ms
  - Increase from Baseline of > 60 ms
- HR
  - Increase from baseline >25% and to a value > 100 bpm
  - Decrease from baseline >25% and to a value < 50 bpm
- PR
  - Increase from baseline >25% and to a value > 200 ms
  - New value of PR > 200 ms
- QRS
  - Increase from baseline >25% and to a value > 120 ms
  - New value of QRS > 120 ms

A newly occurring notable ECG value is defined as an abnormal post-baseline ECG value that is not present at baseline. Baseline is defined as the average of the last ECG measurements (triplicate) taken on or before date of first dose of study treatment. In case ribociclib/placebo dosing time is recorded on the date of first dose of study treatment along with the ECG, the last available assessment before the ricobiclib/placebo start date/time will be used for baseline. The percentage of patients having notable change from baseline ECG values is based on the number of patients with both a baseline and post-baseline assessment.

A listing of all ECG assessments will be produced by treatment arm and notable values will be flagged. A separate listing of only the subjects with notable ECG values may also be produced. In the listing, the assessments collected during the post-treatment period will be flagged.

The safety set will be used for all summary tables and individual listings.

#### 2.7.4.2 Vital signs

Vital sign assessments are performed in order to characterize basic body function. The following parameters were collected: height (cm) (only during screening), weight (kg), body temperature (°C), heart rate (beats per minute), systolic and diastolic blood pressure (mmHg).

#### Data handling

Vital signs collected on treatment will be summarized. Values measured outside of on treatment period will be flagged in the listings.

#### Data analysis

For analysis of vital signs the clinically notable vital sign criteria are provided in [Table 2-6](#) below.

**Table 2-6 Clinically notable changes in vital signs**

Vital sign (unit)	Clinically notable criteria	
	above normal value	below normal value
Weight (kg)	increase > 10% from baseline	decrease > 10% from baseline
Systolic blood pressure (mmHg)	>=180 with increase from baseline of >=20	<=90 with decrease from baseline of >=20
Diastolic blood pressure (mmHg)	>=105 with increase from baseline of >=15	<=50 with decrease from baseline of >=15
Pulse rate (bpm)	>=100 with increase from baseline of >25%	<=50 with decrease from baseline of > 25%
Body temperature	>= 39.1	-

The number and percentage of subjects with notable vital sign values (high only/low only/high and low) will be presented by treatment arm. Summary statistic for change from baseline to the worst post-baseline value (in both directions, i.e. from baseline to highest post baseline and from baseline to lowest post baseline value) will be presented by treatment arm.

A listing of all vital sign assessments will be produced by treatment arm and notable values will be flagged. A separate listing of only the subjects with notable vital sign values may also be produced. In the listing, the assessments collected outside of on-treatment period will be flagged.

## **2.8 Pharmacokinetic endpoints**

Not applicable

## **2.9 PD and PK/PD analyses**

Not applicable

## **2.10 Biomarkers**

Not applicable

## **2.11 Power for analysis of key secondary variables**

Not applicable

## **3 Change to protocol specified analyses**

No change from protocol specified analysis was made.

## **4 Appendix**

### **4.1 Imputation rules**

#### **4.1.1 Study drug**

The following rule should be used for the imputation of the dose end date for ribociclib/placebo:

**Scenario 1:** If the dose end date is completely missing and there is no EOT page and no death date, the patient is considered as on-going:

The patient should be treated as on-going and the cut-off date should be used as the dose end date.

Scenario 1 should not be applicable for final CSR. All patients should have EOT page complete before the Database lock for Final CSR

**Scenario 2:** If the dose end date is completely or partially missing and the EOT page is available:

Case 1: The dose end date is completely missing, and the EOT completion date is complete, then this latter date should be used.

Case 2: Only Year(yyyy) of the dose end date is available and yyyy < the year of EOT date:

**Use Dec31yyyy**

Case 3: Only Year(yyyy) of the dose end date is available and yyyy = the year of EOT date:

**Use EOT date**

Case 4: Both Year(yyyy) and Month (mm) are available for dose end date, and yyyy = the year of EOT date and mm < the month of EOT date:

**Use last day of the Month (mm)**

All other cases should be considered as a data issue and the statistician should contact the data manager of the study.

After imputation, compare the imputed date with start date of treatment, if the imputed date is < start date of treatment:

